#### **11.4.4.2. Secondary Analyses**

Overall and progression free survival will be analyzed using Kaplan Meier techniques. Medians, 25th, and 75th percentiles will be estimated. Selected landmarks for OS (1, 3, 6, and 9 month survival rates) and PFS (1, 3, and 6 month PFS rates) will be estimated from the Kaplan Meier curve. Tumor response and disease control rates will be estimated with proportions and associated 95% Clopper Pearson confidence intervals will be calculated.

#### **11.4.5. Safety Analyses**

Incident rates for adverse events, SAEs, and deaths while on study therapy will be summarized. Laboratory data will be analyzed quantitatively using methods for longitudinal data.

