Laboratory abnormalities are usually not recorded as adverse events; however, signs and/or symptoms that are associated with laboratory findings requiring study withdrawal, dose modification, or medical intervention (e.g., anemia requiring transfusions or hyperglycemia requiring treatment) or other abnormal assessments (e.g., ECG, radiographs, vital signs) must be recorded as adverse events if they meet the definition of an adverse event. In addition, laboratory abnormalities marked as **clinically significant** by the Investigator should also be recorded as adverse events on the eCRF. The Investigator will record the most severe grade of the clinically significant laboratory abnormality and will evaluate its relationship to the study drug and clinical condition if/when a **clinically significant** laboratory abnormality occurs.

The relationship to study drug therapy should be assessed using the following definitions:

**Not Related:** Evidence exists that the AE has an etiology other than the study drug (eg, pre-existing condition, underlying disease, intercurrent illness, or concomitant medication). This includes events that are considered unrelated or unlikely related to study drug.

**Related:** A temporal relationship exists between the event onset and administration of the study drug. It cannot be readily explained by the subject’s clinical state, intercurrent illness, or concomitant therapies. In the case of cessation or reduction of the dose, the event abates or resolves and reappears upon rechallenge. It should be emphasized that ineffective study drug treatment should not be considered as causally

related in the context of AE reporting. This includes events that are considered possibly, probably, or definitely related to study drug.

All adverse events (including event name, grade, start/stop date and attribution) will be documented in the medical record and on the case report form for this protocol.

AEs will be captured from the time of enrollment through 30 days after the date of the last study drug administration.

The Investigator is responsible for verifying and providing source documentation for all adverse events and assigning the attribution for each event for all subjects enrolled on the trial.

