SAEs will be captured from the time of enrollment through 30 days after the date of the last study drug administration. SAEs will be followed until clinical recovery is complete and laboratory tests have returned to baseline, until progression has been stabilized, or until there has been acceptable resolution of the event. This may at times, cause the follow-up period for SAEs to be greater than 30 days. This 30-day time period applies even if the subject is taken off study and enrolled onto another protocol during this time period. Similarly, the Sponsor-Investigator is responsible for following the subject during the required follow-up period even if the subject lives elsewhere or has been released from his or her care and is being treated under another service at LCI.

*Laboratory abnormalities:*

Laboratory abnormalities that meet the definition of a serious adverse event will be recorded as such on the CRF and reported appropriately. The Investigator will record the most severe grade of the clinically significant laboratory abnormality and will evaluate its relationship to the study drug and clinical condition if/when a clinically significant laboratory abnormality occurs.

*Planned hospitalizations:*

Elective surgeries that have been planned prior to subject enrollment in the study or for conditions existing prior to study enrollment do not need to be captured as

SAEs, unless complications occur or the conditions are worse than the subject's baseline. They should however, be clearly documented on the case report form.

*Development of new cancers:*

Secondary malignancies are defined as *new* cancers, not transformations or progression of original disease.

*Secondary malignancies during 30 day time period:*

Any secondary malignancy diagnosed within 30 days of the last dose, regardless of attribution, must be reported as an SAE.

*Secondary malignancies after the 30 day time period:*

Any secondary malignancy diagnosed greater than 30 days after last day of study drug and thought to be possibly, probably or definitely related to drug must be reported as an SAE

*Deaths:*

*Deaths during 30 day time period:*

Any death, expected or unexpected, occurring within 30 days of the last dose of study drug, regardless of attribution, must be reported as an SAE.

*Deaths after the 30 day time period:*

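### Section 11.4.5 plans no summary of laboratory values by CTCAE grade, so Grade 3-4 laboratory toxicity that is not recorded as an adverse event enters no incidence summary

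*Combined protocol and SAP*

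**What the plan says.** Toxicity is a secondary objective (Section 1.2). The introduction to Section 9 lists laboratory changes as a safety variable next to adverse events, and Section 11.2.6 lists laboratory determinations as a safety endpoint separate from them.

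Section 11.4.5 contains the whole safety analysis in two sentences. On events: "Incident rates for adverse events, SAEs, and deaths while on study therapy will be summarized". On laboratory values: "Laboratory data will be analyzed quantitatively using methods for longitudinal data". Neither sentence mentions grade.

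Section 9.2 decides which laboratory findings reach the adverse-event data. The default is that "Laboratory abnormalities are usually not recorded as adverse events". The exceptions are:

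- "signs and/or symptoms that are associated with laboratory findings requiring study withdrawal, dose modification, or medical intervention", where these meet the adverse-event definition;
- "laboratory abnormalities marked as clinically significant by the Investigator should also be recorded as adverse events", for which Section 9.2 adds that "The Investigator will record the most severe grade of the clinically significant laboratory abnormality";
- in Section 9.4, "Laboratory abnormalities that meet the definition of a serious adverse event will be recorded as such on the CRF and reported appropriately".

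Section 4.3.7 schedules a complete blood count and a comprehensive metabolic panel every 2 weeks after enrollment. Amylase, lipase and the coagulation panel are scheduled at screening only. CTCAE v4.0 is the grading scale (Sections 7.3 and 9).

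**The concern.** A safety reader of a 32-subject single-arm study asks how many subjects reached Grade 3 or 4 for ALT, bilirubin, neutrophils or platelets, and from what baseline. Methods for quantitative values over time describe trends and do not by themselves give that count. The count would have to come from the adverse-event data, where entry rests largely on an Investigator's judgement in an open-label study and no grade threshold applies.

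Baselines will also differ. Section 3.1 admits subjects with ALT and AST up to 5 x ULN if they have malignant liver involvement or a biliary stent, so pooled values are hard to read without a shift from baseline. At stake is whether the laboratory part of the toxicity objective can be reported completely from what the plan specifies.

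**Working it through.** The plan gives no laboratory figure to reproduce. Its design figure does reproduce: rejecting at 8 or more of 32, the exact binomial type I error at 0.15 is 0.0958 and the power at 0.35 is 0.918. Nothing below alters either.

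**Step 1: trace a Grade 3-4 value through the plan.**

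| Type of Grade 3-4 value | Route into the adverse-event or SAE data | In a planned incidence summary? |
|---|---|---|
| Meets an SAE criterion | 9.4 | Yes |
| Marked clinically significant | 9.2, with worst grade | Yes |
| Requires withdrawal, dose modification or intervention, with signs or symptoms | 9.2 | Yes |
| Requires one of these, without symptoms, not marked | 9.2, depending on reading | Unclear |
| Asymptomatic, not marked, not serious, no action required | None | No |

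The fourth row is unclear because the clause literally covers the associated signs and symptoms, while its examples (anemia needing transfusion, hyperglycemia needing treatment) are themselves laboratory-defined. The fifth row is the gap. Footnote b of Table 7.1 takes asymptomatic laboratory abnormalities out of the dose-modification rule, so for blood counts the dose-modification route does not help an asymptomatic value.

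**Step 2: show what a gap of a given size would do.** The documents give neither the true Grade 3-4 laboratory rate p nor the share s that reaches the adverse-event data. Both are assumptions here, shown over a range. With n = 32:

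- expected subjects in the adverse-event data = n × p × s
- chance that the adverse-event data show none = (1 − p × s)^n

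| p | s = 100% | s = 75% | s = 50% | s = 25% |
|---|---|---|---|---|
| 10% | 3.2 (3.4%) | 2.4 (8.3%) | 1.6 (19.4%) | 0.8 (44.5%) |
| 20% | 6.4 (0.1%) | 4.8 (0.6%) | 3.2 (3.4%) | 1.6 (19.4%) |
| 30% | 9.6 (<0.1%) | 7.2 (<0.1%) | 4.8 (0.6%) | 2.4 (8.3%) |

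Each cell gives the expected number of subjects and, in parentheses, the chance of none. For example, with p = 10% and s = 50%: 32 × 0.10 × 0.50 = 1.6 and 0.95^32 = 0.194.

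One rate in the documents helps with scale. Section 2.2.2 cites 8% Grade 3+ hyperbilirubinemia on regorafenib in the colorectal trial. That is another disease and is itself an adverse-event rate, so using it as p is an assumption. It gives 32 × 0.08 = 2.56 expected subjects. The chance of seeing none is 0.92^32 = 6.9% at s = 100%, 0.94^32 = 13.8% at 75%, 0.96^32 = 27.1% at 50% and 0.98^32 = 52.4% at 25%.

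**Step 3: precision of the proposed table.** 95% Clopper-Pearson intervals with n = 32 are 0 to 10.9% for 0/32, 2.0 to 25.0% for 3/32 and 7.2 to 36.4% for 6/32. The rates will be imprecise, and with counts this small one or two missing subjects change the reported picture.

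**The case against.** The exceptions in Sections 9.2 and 9.4 are the routes most likely to catch severe laboratory events. A drug-related Grade 3 rise in ALT, AST or bilirubin calls for delay and dose reduction under Table 7.5, and Section 7.5 documents interruption and reduction as actions taken for an adverse event. Such a rise would probably be recorded. For other values, Section 7.2.1, Table 7.1 footnote b and Section 6.1.1.2 act on clinically significant toxicity, which is close to the filter in Section 9.2. Sections 8.1 and 8.2 add at least monthly safety review with the Study Statistician, and source-to-CRF monitoring. All of this stands, and it limits the likely size of the gap. None of it makes grade a condition for entry or provides a graded summary.

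Three stronger readings are tempting, and the documents do not support them.

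- *That laboratory toxicity is analysed only by longitudinal methods, or that the rates are biased low as a fact.* Flagged abnormalities with their worst grade and laboratory SAEs do reach the incidence summary. The capture share is unknown.
- *That dropout will distort mean laboratory curves.* With exponential PFS and the plan's 6-week null median, 1 − 0.5^(4/6) = 37% have a PFS event by week 4 and 1 − 0.5^(8/6) = 60% by week 8. These are not laboratory dropout rates: the first on-treatment scan is at week 8 ± 2 (Section 4.3.8), so radiologic progression before it does not stop the two-weekly tests. The plan also commits to no mean model; longitudinal methods include models for graded outcomes.
- *That grade alone drives treatment throughout the plan.* This fits Table 7.5 but not Table 7.1, given its footnote b.

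A further fair point is that worst-grade counts regardless of cause mix disease effects with drug effects. Section 7.2.5 applies Table 7.5 only where no alternative cause, such as cholestasis or progression, is evident. The proposed table therefore has to be labelled as regardless of attribution and read next to the adverse-event data.

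**Conclusion.** The point holds as a gap in specification. A Grade 3-4 laboratory value that is asymptomatic, unflagged and not serious enters no planned incidence summary, so Grade 3-4 laboratory rates reported for the toxicity objective may be understated. The amount cannot be estimated from the documents; the illustrative counts rest wholly on assumed rates and capture shares. The conclusion rests on reading Section 11.4.5 as the complete safety analysis and Sections 9.2 and 9.4 as the complete rules for entry. It is a modest reporting matter that does not touch the primary test, and a low-cost improvement is available.

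**What to change.** Add to Section 11.4.5, in substance: for all treated subjects and each CTCAE v4.0-gradable parameter measured after baseline (complete blood count and comprehensive metabolic panel, including unscheduled values), the grade will be derived from the laboratory value regardless of attribution. Worst post-baseline grade and the shift from baseline to worst grade will be tabulated, with 95% Clopper-Pearson intervals for the proportion with Grade 3-4. The tables will be presented alongside the adverse-event summary, where attribution is recorded. The longitudinal analysis is kept as descriptive, with its method named.

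Include amylase, lipase and coagulation only where unscheduled post-baseline values exist. The listing of coagulation as a safety variable in Section 9 and the screening-only schedule in Section 4.3.7 must be reconciled.

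Cost: some extra programming on values already collected, with no new visits or tests. Toxicity may look less favourable, and the counts will combine disease-related and drug-related abnormalities.

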#### **11.4.6. Exploratory Analyses**

Cox proportional hazards models and logistic regression will be used to assess the correlation between baseline characteristics and biomarker expression levels with clinical outcomes.

### **11.5. Interim Analyses**

No interim analyses are planned for this study.

## **12. STUDY COMPLETION AND TERMINATION**

### **12.1. Completion**

The study will be considered complete when one or more of the following conditions is met:

- All subjects have completed all study visits.
- All subjects have discontinued from the study.
- The IRB, LCI DSMC, Sponsor-Investigator or Bayer HealthCare discontinues the study because of safety considerations.
- The Sponsor-Investigator defines an administrative or clinical cut-off date.

## **12.2. Termination**

The study will be terminated when one or more of the following conditions occur:

If risk-benefit ratio becomes unacceptable owing to, for example:

- Safety findings from this study (e.g. SAEs)
- Results of any interim analysis
- Results of parallel clinical studies
- Results of parallel animal studies (e.g. toxicity, teratogenicity, carcinogenicity or reproduction toxicity).
- If the study conduct (e.g. recruitment rate; drop-out rate; data quality; protocol compliance) does not suggest a proper completion of the trial within a reasonable time frame.

The Sponsor-Investigator has the right to close the trial at any site and at any time.

For any of the above closures, the following applies:

- Closures should occur only after consultation between involved parties.
- All affected institutions must be informed as applicable according to local law.
- In case of a partial study closure, ongoing subjects, including those in follow-up, must be taken care of in an ethical manner.

Details for individual subject's withdrawal can be found in Section 3.4.

## **13. RETENTION OF RECORDS**

Essential documentation (e.g. adverse events, records of study drug receipt and dispensation), including all IRB correspondence, will be retained for at least 2 years after the investigation is completed. Documentation will be readily available upon request.

## **14. ETHICAL AND LEGAL ISSUES**

### **14.1. Ethical and Legal Conduct of the Study**

The procedures set out in this protocol, pertaining to the conduct, evaluation, and documentation of this study, are designed to ensure that the Investigator abide by Good Clinical Practice (GCP) guidelines and under the guiding principles detailed in the Declaration of Helsinki. The study will also be carried out in keeping with applicable local law(s) and regulation(s).

Documented approval from appropriate agencies (e.g. DSMC, IRB) will be obtained for all participating centers before start of the study, according to GCP, local laws, regulations and organizations. When necessary, an extension, amendment or renewal of IRB approval must be obtained and forwarded to Bayer HealthCare.

Strict adherence to all specifications laid down in this protocol is required for all aspects of study conduct; the Investigators may not modify or alter the procedures described in this protocol.

Modifications to the study protocol will not be implemented by the Sponsor-Investigator without discussion and agreement by Bayer Healthcare. However, the Investigators may implement a deviation from, or a change of, the protocol to eliminate an immediate hazard(s) to the trial subjects without prior approval from applicable agencies. As soon as possible, the implemented deviation or change, the reasons for it and if appropriate the proposed protocol amendment should be submitted to the appropriate agencies. Any deviations from the protocol must be explained and documented by the Investigator.

The Sponsor-Investigator is responsible for the conduct of the clinical trial at the sites in accordance with Title 21 of the Code of Federal Regulations and/or the Declaration of Helsinki. The Sponsor-Investigator is responsible for personally overseeing the treatment of all study subjects. The Sponsor-Investigator must assure that all study site personnel, including sub-investigators and other study staff members, adhere to the study protocol and all applicable regulations and guidelines regarding clinical trials both during and after study completion.

The Sponsor-Investigator will be responsible for assuring that all the required data will be collected and properly documented.

## **14.2. Confidentiality**

All records identifying the subject will be kept confidential and, to the extent permitted by the applicable laws and/or regulations, will not be made publicly available.

## **15. PUBLICATION POLICY**

The Sponsor-Investigator must send a draft manuscript of the publication or abstract to Bayer HealthCare prior to submission of the final version for publication or congress presentation. All relevant aspects regarding data reporting and publication will be part of the contract between Bayer HealthCare and the Sponsor-Investigator.

The Sponsor-Investigator will ensure that the information regarding the study be publicly available on the internet at [www.clinicaltrials.gov](http://www.clinicaltrials.gov).

## APPENDICES

### APPENDIX A: EXAMPLES OF A LOW-FAT MEAL

Two slices of white toast with 1 tablespoon of low-fat margarine and 1 tablespoon of jelly and 8 ounces (240 mL) of skim milk (approximately 319 calories and 8.2 g of fat).

One cup of cereal (i.e. Special K), 8 ounces (240 mL) of skim milk, one piece of toast with jam (no butter or marmalade), apple juice, and one cup of coffee or tea (2 g fat, 17 g protein, 93 g of carbohydrate, 520 calories).

**APPENDIX B: PERFORMANCE STATUS CRITERIA**

ECOG Performance Status Scale	
Grade	Descriptions
0	Normal activity. Fully active, able to carry on all pre-disease performance without restriction.
1	Symptoms, but ambulatory. Restricted in physically strenuous activity, but ambulatory and able to carry out work of a light or sedentary nature ( e.g. , light housework, office work).
2	In bed <50% of the time. Ambulatory and capable of all self-care, but unable to carry out any work activities. Up and about more than 50% of waking hours.
3	In bed >50% of the time. Capable of only limited self-care, confined to bed or chair more than 50% of waking hours.
4	100% bedridden. Completely disabled. Cannot carry on any self-care. Totally confined to bed or chair.
5	Dead.
